10 MEASUREMENT	
10.1 Primary and Secondary Outcome measures	24
10.2 Stopping Rules	24
11 REGULATORY CONSIDERATIONS	25
11.1 Institutional Review of Protocol	25
11.2 Data Management Plan	25
12 STATISTICAL CONSIDERATIONS	25
13 REFERENCES	_
APPENDIX A: Graft-Versus-Host Disease Grading	31
APPENDIX B: Current Criteria Used at Stanford University at the Adult and Pediatric Programs Stem Cell	
Transplantation Programs to establish Graft Failure	33

Protocol Synopsys:

Synopsys:									
Principal Investigator at	[name].								
Stanford	[name]. Mail Code:								
	[contact]. [contact]. [contact]								
Funding Source	None.								
Protocol Title	An Expanded Access Study Using the CliniMACS [®] System to Offer Therapeutic Manipulated Grafts that are CD34+ Cell Enriched and T Cell Depleted for Allogeneic Stem Cell recipients with Matched or Mismatched Related Donors or with Borderline Organ Function								
Clinical Phase	Phase II								
Cillical Phase	Hypothesis: Transplantation of stem cells that have been CD34+ selected and T cell-depleted with the CliniMACS [®] device will prevent severe (grade III/IV) acute GvHD without the use of prophylactic post-transplant immunosuppression. The incidence of grade III/IV acute GVHD is predicted to be <10% after cell manipulation. Background: The CliniMACS® System (Device, Reagents, Tubing Sets, Instruments and PBS/EDTA Buffer) is manufactured and controlled under an ISO 13485 and ISO 9001 certified quality system. In Europe, the CliniMACS System and Reagents are available as CE-marked medical devices for use in humans. Inthe USA, CliniMACS® System is available for use only under an approved Investigational New Drug (IND) application or Investigational Device Exemption (IDE). Its safety has been tested in multiple eIND and eIDE FDA submissions. As of 2011, eighty four IDE protocols utilize the CliniMACS® CD34 Reagent to select CD34+ cells from heterogeneous hematologic cell populations. In 2011, Miltenyi Biotech HDE submitted CliniMACS® CD34 Reagent System as a Humanitarian Use Device (HUD) in its Registration Pathway in the U.S. Clinical data from BMT								
Background and Rationale	CTN 0303 Clinical — a phase II multi-center clinical trial sponsored by the BMT CTN (BB-IDE 11965) which enrolled 47 Acute Myeloid Leukemia (AML) patients after myeloablative therapy for HLA-matched allogeneic stem cell transplant recipients, without additional GvHD prophylaxis from October 2005 to December 2008 — supports "safety" and "probable benefit" arguments of the CliniMACS System. In January, 2014, the CliniMACS CD34 Reagent System received FDA approval as a Humanitarian Use Device for processing hematopoietic progenitor cells collected by apheresis from an allogeneic, HLA-identical, sibling donor to obtain a CD34+ cell-enriched population for hematopoietic reconstitution following a myeloablative preparative regimen without the need for additional GvHD prophylaxis in acute myeloid leukemia. (44) Rationale: Hematopoietic stem cell transplantation (HSCT) is now recognized as an effective form of therapy for an increasing number of malignant and non-malignant disorders. Therefore, extending the donor pool to alternative source of hematopoietic stem cells (HSCs) that is capable of reconstituting hematopoiesis after intensive myeloablative therapy is an important goal in this field. The preferred donor for an allogeneic HSCT is an HLA identical sibling. However, less than 25% of patients requiring a transplant will have such a donor. The purpose of this protocol is to provide access to the CliniMACS® System to patients who only have donors with a significant HLA-mismatched compatibility (alternative donors) or have a matched related donor but cannot receive post immunosuppressive therapy due to organ function. By manipulating the product graft through this platform, we can offer a CD34 enriched and T-cell depleted graft that addresses the main morbidity and mortality issue for this type of hematopoietic stem cell transplant (HSCT): overwhelming (grade III/IV) graft-versus-host disease (GvHD). The cell manipulation provides cellular therapeutic GvHD prophylaxis, therefore								

	eliminating the need of post-HSCT immunosuppressant therapies making this process also a viable alternative to deliver a life-saving HSCT for patients who do not have a matched related donor and for those with borderline organ function who might not endure the often-toxic side-effects of traditional post-HSCT immunosuppressive therapy.
Objectives	This is a prospective study to provide access to an investigational device and reagents used for progenitor cell sorting of a stem cell transplant donor graft to determine the ability of CD34+ cell selection and T Cell depletion (using the
Objectives	CliniMACS [®] device as the sole GvHD prophylaxis) to prevent severe (grade III-IV) acute GvHD in recipients of mismatched related or unrelated donor hematopoietic stem cell transplants or with borderline organ function who might not endure the often toxic side-effects of traditional post-HSCT immunosuppressive therapy.
Primary Endpoint(s)	The primary endpoint of the study is the incidence of severe (grade III/IV) acute GvHD occurring by Day +100 after transplant.
Secondary Endpoint(s)	Outcomes measures for the secondary endpoints will include: Engraftment: The incidence of primary graft failure and graft rejection will be determined. Chimerism at Day 100: The percentage of donor cells will be reported for all evaluable (without disease progression) patients. Immune recovery: The time to CD4 count >100 and > 200 and PHA≥ 10% and 30% will be calculated. Severe toxicities: The incidence of severe toxicities will be determined. This will include grade 3/4 stem cell product infusion-related toxicity. Post-transplant infections (bacterial, viral and fungal): Post-transplant infections will be described by incidence and type. Post-transplant lymphoproliferative disease (PTLD): The incidence of PTLD will be calculated. Transplant-related mortality (TRM): The incidence of TRM will be calculated at Day 100 after transplant and at one year. Disease-free survival. Overall survival: Overall survival will be estimated using the Kaplan-Meier method. Device (CliniMACS®) performance parameters: The parameters will be summarized for all products that are processed and median and ranges will be determined.
Study Design	Participants will be enrolled with alternative (mismatched/haplocompatible) related/unrelated donors or matched related/unrelated donors for an initial HSCT.
Study Centers	This is a Stanford University, Principle Investigator (PI) initiated protocol conducted at LPCH and Stanford Hospital and Clinics.
Duration of Study per Subject	Individual participants will be followed for outcomes related to the experimental device including acute and chronic GvHD and engraftment for a minimum of one year. Subsequent follow-up care will follow the standard for all transplant patients.
Subject Population	Pediatric and adult patients up to 35 years old, of any gender, and ethnic background, with malignant and/or non-malignant diagnosis that are treatable though allogeneic stem cell transplantation.

Inclusion Criteria:

- Participants greater than one month of age.
- Participant has a disorder that can be treated with a hematopoietic stem cell transplant
 - Participant's is eligible for an allogenic HSCT as per current institutional SOP and FACT standards
- Participant must have a related or unrelated matched or mismatchedrelated donor who is:
 - Able to receive granulocyte colony-stimulating factor (G-CSF) and undergo apheresis either through placement of catheters in antecubital veins or a temporary central venous catheter OR agrees on a bone marrow harvest;
 - Healthy as per donor selection screening (following current SOP based on standards of foundation for accreditation of cellular therapy and stem cell transplantation – FACT);
 - Willing to participate and sign consent.
- Participant or Legal Authorized Representative is able to sign informed consent (and signed assent, if applicable) for transplant.

Exclusion Criteria:

- Participant does not qualify for an allogeneic transplant due to medical screening, underlying disease, or lack of alternative donors.
- Any condition that compromises compliance with the procedures of this protocol, as judged by the principal investigator.

Principal Investigator will evaluate and report all grade 3 or 4 adverse reactions that are unexpected and possibly related to the investigation in process and are not expected TRM as per protocol definition. If it becomes clear that the study treatment is less effective than other available treatments or the toxicity is unacceptable we will follow the stopping rules.

Stopping rule for primary graft failure: The first 30 enrolled patients (related and unrelated) will be evaluated for the stopping rule for primary graft failure. The trial is stopped if there are ≥ b graft failures out of k resolved patients. Only points where stopping is possible are listed.

Discontinuation Criteria (Safety Considerations)

Eligibility criteria

k	2	4	5	6	8	9	10	12	13	14	15	16	18	19	20	21	23	24	25	26	27	28	30
b	2	3	3	3	4	4	4	5	5	5	5	5	6	6	6	6	7	7	7	7	7	7	8

The stopping rule for graft failure yields the probability of stopping the trial of 0.05 if the rate of graft failure is 0.1. The probability of stopping the trial is 0.41 if the graft failure rate is 0.2, 0.82 if the graft failure rate is 0.3, and 0.96 if the graft failure rate is 0.4. These probabilities were calculated based on the binomial distribution.

If the study reaches a stopping boundary, the study will be suspended. Proper use of the stopping rule table will be ensured by the Study Investigator.

Stopping rule for Grade \geq IV toxicity: If any patient develops grade \geq IV acute GvHD, grade \geq IV infection, or any unexpected grade \geq IV toxicity by 4 weeks post-transplant, the protocol will be halted and the processing re-evaluated before

	proceeding.
	Conditions for individual patient termination: Disease progression Need for exclusionary concurrent treatment (per PI discretion) Withdrawal of informed consent Protocol non-compliance
	The PI, through the reports from the Stem Cell Laboratory, will also monitor system performance based on: Cellular composition of final product Yield (% recovery) of CD34+ cells from the starting product CD3+ cell reduction Sterility Purity
Sample Size	The study will enroll 30 transplant recipients at Stanford.
Statistical Methodology	Statistical analysis results will be reported using summary tables, figures, and data listings. Continuous variables will be summarized using the mean, standard deviation, median, minimum, and maximum. Categorical variables will be summarized by numbers and percentages of subjects in corresponding categories. All raw data obtained from the case report form (CRF) and any derived data will be summarized and included in data listings. Missing data will not be imputed.

List of Abbreviations and Definition of Terms

List of Abbreviations	List of Appreviations and Definition of Terms
AE	Adverse event
AdV	Adenovirus
aGvHD	Acute Graft-versus-Host Disease
ALL	Acute Lymphoblastic Leukemia
Allo	Allogeneic
AML	Acute Myelogenous Leukemia
ANC	Absolute Neutrophil Count
ВМ	Bone marrow
BM bx.	Bone marrow biopsy
ВМІ	Body mass index
BMT	Bone Marrow Transplant
BP	Blood pressure
BSA	Body surface area
°С	Degrees Celsius
СВ	Cord blood
CBC	Complete blood count
CD	Cluster of Differentiation
CFR	Code of Federal Regulations
cGvHD	Chronic Graft-versus-Host Disease
CIBMTR	Center for International Blood and Marrow Transplant Research
CML	Chronic Myelogenous Leukemia
CMV	Cytomegalovirus
CNS	Central nervous system
Co-PI(s)	Co-Investigator(s)
CRF	Case report/record form
CR	Complete response
CTCAE	Common Terminology Criteria for Adverse Events
CTN	Clinical Trials Network
DFS	Disease Free Survival
DLI	Donor Leukocyte Infusion
DLT	Dose Limiting Toxicity
DSMB	Data Safety Monitoring Board
DSMC	Data and Safety Monitoring Committee
EBV	Epstein Barr Virus
EC	Ethics Committee
ECG	Electrocardiogram
Echo/ECCO	Echocardiogram

EFS	Event-free survival
EIDE	Emergency investigational device exemption
EIND	Emergency Investigational new drug
F	Fahrenheit
FA	Fanconi Anemia
FACT	Foundation for the Accreditation of Cellular Therapy
FDA	Food and Drug Administration
GCP	Good clinical practice
G-CSF	Human granulocyte-colony stimulating factor
GI	Gastrointestinal
GFR	Glomerular filtration rate
GvHD	Graft-versus-Host Disease
HBV	Hepatitis B Virus
HCG	Human chorionic gonadotropin
HCV	Hepatitis C Virus
Hgb	Hemoglobin
HIV	Human Immunodeficiency Virus
HHV	Human Herpes Virus
HLA	Human leukocyte antigen
HPF	High-power field
HR	Heart rate
HSCs	Hematopoietic stem cells
HSCT	Hematopoietic Stem Cell Transplant
HSV	Herpes Simplex Virus
HTN	Hypertensions
HUD	Humanitarian Use Device
IB	Investigator Brochure
IDE	Investigational Device Exemption
IND	Investigational New Drug
IRB	Institutional Review Board
IV	Intravenous
LAR	Legal authorized representative
LLN	Lower limit of normal
LN ₂	Liquid Nitrogen
mAb	Monoconal antibody
MDS	Myelodysplastic Syndrome
MRD	Matched related donor
NCI	National Cancer Institute
NCI CTCAE	National Cancer Institute common terminology criteria for adverse events
NHL	Non-Hodgkin's Lymphoma

NIH	National Institutes of Health
NK	Natural killer
NMDP	National Marrow Donor Program
OS	Overall survival
PBSC	Peripheral blood stem cells
PCR	Polymerase chain reaction
PD	Progressive diseased
Peds	Pediatric patients
PFS	Progression free survival
PI	Principal investigator
PLT	Platelet
PMRD	Partially matched donor
PPA	Per protocol analysis
PR	Partial response
PTLD	Post-transplant lymphoproliferative disorder
RR	Response rate
SAE	Serious adverse event
SCCI	Stanford Center for Clinical Informatics
SD	Stable disease
SCT	Stem cell transplant
SCTT	Stanford Blood and Marrow Cellular Therapeutics & Transplantation Laboratory
SOP	Standard Operating Procedure
SRC	Scientific Review Committee
T. bili	Total bilirubin
TBI	Total body irradiation
TRM	Transplant-related mortality
TTP	Time to progression
UCB	Umbilical Cord Blood
ULN	Upper limit of normal
UNK	Unknown
URD	Unrelated donor
VZV	Varicella Zoster Virus
WBC	White blood cell
WHO	World Health Organization

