1.0 OBJECTIVES

A major issue in alternative donor (mismatched related and unrelated donor) transplantation is the development of graft-versus-host disease (GvHD). For those who cannot receive post-transplant immunosuppressive therapy, any form of graft versus host disease, even with a matched related or unrelated donor can also be a complication. Several clinical trials have shown that the use of T cell-depleted peripheral blood stem cells (PBSC) reduces GvHD in hematopoietic stem cell transplants (HSCT). By using a purified stem cell graft, there is a reduced risk of post-transplant graft versus host disease in patients who have a mismatched donor or cannot receive post-transplant immunosuppression.

This is a prospective study to provide access to an investigational device and reagents used for progenitor cell sorting. The hypothesis is that the CliniMACS® System will allow for a manipulated graft – with augmented CD34+ cells and T cell-depleted numbers --- in a ratio that will prevent severe (grade III/IV) acute GvHD (as defined on appendix C) without the use of prophylactic post-transplant immunosuppression. The incidence of grade III/IV acute GVHD is predicted to be lesser than 10% based on similar ongoing trials (17).

The objective is to manipulate (alter the ratio) specific cells in the donor graft to determine the ability of augmented CD34+ cells and T cell-depleted products to prevent severe (grade III/IV) acute GvHD in recipients of mismatched related donor hematopoietic stem cell transplants as well as to candidates of allogeneic (allo) transplant with borderline organ function -- who might not endure the often toxic side- effects of traditional post-HSCT immunosuppressive therapy.

The patients will receive conditioning therapy based on their diagnosis and per instructional guidelines for treating the disease. The transplant recipients will be followed for one year post- transplant for the development of GvHD, engraftment, post-transplant infections, disease relapse, and overall survival.

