2.3 Rationale

Cell dose is the most important factor affecting clinical outcomes in adult patients undergoing transplantation. Transplantation with a cell dose of less than 2.5×10^7 nucleated cells per kilogram or a CD34 dose of less than 1.7×10^5 per kilogram is associated with higher rates of non-engraftment, non-relapse mortality and lower survival (14). Alternative donors can provide ideal cell dose grafts and have the advantage of being rapidly available, but the higher probabilities of severe acute and extensive chronic GvHD due to HLA-mismatched is a significant source of morbidity and mortality. This study provides access to a model that potentially benefits from alternative NMDP and related donor pools to test the safety and efficacy of manipulated grafts using the CliniMACS® System. The aim is to ensure robust cell dose grafts with the best available donor for allogeneic HSCT recipients while providing a method for T cell depletion through CD34+ selection as the single form of GvHD prophylaxis. Currently, there is not a FDA-approved method for this process in the United States.

The outcomes in relatively small studies for children receiving unrelated donor transplants using the CliniMACS® have been comparable to or better than those receiving T cell depleted transplants with post-transplant immunosuppression (21, 25). This study will enroll up to 30 transplant recipients at Stanford. As the recommended prescription of allogeneic transplantation for different underlying diseases grows, enrollment on this protocol is expected to gradually increase in relation to the overall number of transplants performed in our center.

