12 STATISTICAL CONSIDERATIONS

Interim descriptive analyses will be performed annually. As the eligibility for this protocol is very broad, analyses will be done separately for several pre-specified subgroups.

First, analyses will be conducted separately for patients transplanted for malignant diseases and those transplanted for non-malignant diseases. They will also be analyzed separately for transplants using mismatched related versus alternative donors. Finally, analyses will be conducted separately for primary vs. secondary allogeneic transplants. Further separation of the study population such as adults vs. pediatrics and myeloablative vs. non-myeloablative conditioning regimens will be considered depending on the patient numbers. In particular, neutrophil and platelet engraftment will only be analyzed using transplants with myeloablative conditioning regimens.

Baseline characteristics will be described using frequencies/percent or median/range as appropriate.

The study will enroll 30 transplant recipients at Stanford. As the recommended prescription of allogeneic transplantation for different underlying diseases grows, enrollment on this protocol is expected to gradually increase in relation to the overall number of transplants performed in our center.

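### The primary endpoint is to be summarised by numbers and percentages alone; with 30 recipients the predicted rate below 10% cannot be discussed without a pooled incidence and an exact confidence interval

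*Combined protocol and SAP*

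**What the plan says.** The synopsis, under its hypothesis, gives a number: "The incidence of grade III/IV acute GVHD is predicted to be <10% after cell manipulation". Section 1.0 repeats the prediction and attributes it to similar trials, citing reference 17. The endpoint row of the synopsis reads: "The primary endpoint of the study is the incidence of severe (grade III/IV) acute GvHD occurring by Day +100 after transplant".

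On analysis, the Statistical Methodology row of the synopsis says: "Categorical variables will be summarized by numbers and percentages of subjects in corresponding categories". Section 12 adds annual descriptive interim analyses and then states: "As the eligibility for this protocol is very broad, analyses will be done separately for several pre-specified subgroups". The subgroups it lists are disease type (malignant or not), donor type, and first versus later allogeneic transplant, with further splits if numbers allow. Section 12 mentions neither the GvHD endpoint nor the 10% figure.

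On size, Section 12 says "The study will enroll 30 transplant recipients at Stanford", while Section 2.3 says "This study will enroll up to 30 transplant recipients at Stanford". Neither place ties the number to alpha, power or precision for GvHD. The only operating characteristics in the document belong to the graft-failure stopping rule (synopsis and Section 10.2).

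**The concern.** A numeric prediction and a primary endpoint measured against it call for a statement of uncertainty, and the plan provides none. If 1 or 2 of 30 recipients have grade III/IV disease, the planned output is 3.3% or 6.7%. Both lie below 10%, and nothing in the planned reporting would show that rates well above 10% are also compatible with those data. The analyses Section 12 does name divide the 30 further, so each of those percentages carries still less information.

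At stake is how the main GvHD result is read. The stopping rules do not fill the gap: one monitors graft failure, and the other halts the protocol on a single grade IV event by 4 weeks. Neither compares the Day +100 grade III/IV incidence with 10%.

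**Working it through.** **Inputs.** n = 30 (Section 12); threshold 10% (synopsis and Section 1.0); endpoint a yes/no event by Day +100 (synopsis). The document gives no alpha or interval level for this endpoint, so the conventional 95% is my assumption.

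**The plan's own figures.** There is none to reproduce for GvHD. As a check on method, an exact sequential binomial calculation over the printed graft-failure boundary gives stopping probabilities of 0.049, 0.408, 0.827 and 0.978 at failure rates of 0.1, 0.2, 0.3 and 0.4. The stated values are 0.05, 0.41, 0.82 and 0.96, all within 2 points. (The 0.41 there is unrelated to the 0.41 below.)

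**Largest count with an observed rate below 10%.** 3/30 is exactly 10%, so it is 2/30 = 6.7%.

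**Chance of seeing 2/30 or fewer.** P(X ≤ 2) = Σ C(30, x) pˣ (1 − p)³⁰⁻ˣ for x = 0, 1, 2. At p = 0.10:

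- x = 0: 0.9³⁰ = 0.042
- x = 1: 30 × 0.1 × 0.9²⁹ = 0.141
- x = 2: 435 × 0.01 × 0.9²⁸ = 0.228
- Sum: 0.411

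The same sum is 0.285 at a true 12%, 0.151 at 15% and 0.044 at 20%.

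**Exact (Clopper-Pearson) two-sided 95% interval.** The lower limit is the 0.025 quantile of Beta(x, 31 − x), or 0 when x = 0. The upper limit is the 0.975 quantile of Beta(x + 1, 30 − x). For x = 0 the upper limit is 1 − 0.025^(1/30) = 0.116.

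| Events | Observed | 95% interval |
|---|---|---|
| 0/30 | 0% | 0 to 11.6% |
| 1/30 | 3.3% | 0.1 to 17.2% |
| 2/30 | 6.7% | 0.8 to 22.1% |
| 3/30 | 10.0% | 2.1 to 26.5% |

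No result at n = 30 has an upper limit below 10%. That would need at least 36 recipients with no event, 54 with one, or 70 with two.

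**Subgroups.** Their sizes are not given, so I assume 10 to 20. With no events at all, the two-sided upper limit is 30.8% for 0/10, 21.8% for 0/15 and 16.8% for 0/20.

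**Sensitivity to the denominator.** Section 2.3 makes 30 a ceiling. If fewer are evaluable, the chance of an observed rate below 10% at a true 10% is 0.54 for 2/25 or fewer and 0.39 for 1/20 or fewer.

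**The case against.** The strongest reply is that the plan predicts a rate but tests nothing. A reader might infer that 2/30 or fewer would be declared a confirmation, so that the trial has a 41% false-confirmation rate. The documents do not support that: no section attaches a success criterion, a test or a conclusion to 10%. The 0.41 describes how often the observed percentage falls below 10% when the true rate is 10%; it is not the error rate of a rule the protocol sets. It is also taken at the threshold itself, where any comparison of a point estimate does poorly. At a true 20% the probability is only 0.044, so the data do carry information against high rates.

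A reader might also infer that no study-wide estimate is intended. That goes too far. The synopsis defines one incidence for the study, with no subgroup restriction, so a pooled percentage is implied even though Section 12 does not name it.

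Finally, this is titled an expanded access study and its stated purpose is to provide access, so descriptive reporting is defensible. That stands. But the synopsis also calls it Phase II and states a hypothesis, and Section 1.1 sets out to determine whether the method prevents severe GvHD. A descriptive estimate from 30 patients still needs an interval, and asking for one does not impose a confirmatory test.

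**Conclusion.** The point holds as a weakness in the planned analysis and reporting of the primary endpoint. Numbers and percentages alone, with only subgroup analyses named, would let a result of 1/30 or 2/30 stand without showing that rates up to 17.2% or 22.1% are not excluded. It does not hold as a claim that the protocol contains a faulty decision rule, because it contains none.

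The figures assume 30 recipients, all classified for the event by Day +100, with independent outcomes. Given the broad eligibility, the pooled rate is an average over the case mix actually enrolled. The document has no rule for recipients who die or leave before Day +100 without the event; counting them in the denominator as event-free is a convention the plan would need to state.

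**What to change.** Add to Section 12:

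- The primary analysis is the number of recipients with grade III/IV acute GvHD by Day +100 divided by all transplanted recipients, pooled, with an exact (Clopper-Pearson) two-sided 95% confidence interval.
- Recipients who die or leave before Day +100 without the event remain in the denominator, and their number is reported.
- Wherever the report discusses the predicted rate below 10%, it states the highest rate not excluded, that is, the upper limit of that interval.
- Subgroup incidences are descriptive, each with an exact confidence interval.

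Keep n = 30. I would not add a rule that claims a rate below 10% only after 0/30. It rests on a one-sided 95% upper limit of 9.5% and would be reported beside a two-sided interval reaching 11.6%. It would be met with probability only 0.21 at a true 5% and 0.55 at a true 2%, the rate Section 2.1 quotes from reference 17.

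The cost is a few lines of text and no extra patients. The downside is a more modest conclusion: at this size the report can say the data are consistent with a rate below 10%, but not that they show it.

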Infections were common. All patients were at risk for CMV reactivation. Seven patients (39%) reactivated CMV. All cases were responsive to anti-viral therapy and/or DLI. No CMV disease was seen. Seven patients had adenovirus reactivation and six had HHV-6 reactivation. EBV reactivation occurred in 5/18 (28%) patients, three of whom manifested signs of post-transplant lymphoproliferative disorder.

Patients received a median of 3×10^4 CD3+ cells/kg at the time of transplant. Some patients received additional donor T cells (DLI) for viral reactivation. At three months post-transplant, only 4 of the 15 evaluable patients had a CD4 count > 100. By nine months post-transplant, 10 of the 13 evaluable patients had a CD4 count > 200.

There is an ongoing study at the University of California, San Francisco Medical Center of a prospective trial of CD34+ selected (with the CliniMACS® device) PBSC from mismatched related donors (protocol CC# 01151). Patients received a conditioning regimen including TBI 1200 cGy, thiotepa, fludarabine, and rabbit-ATG (3.5 mg/kg). Patients received a fixed T cell dose of 3 x 10⁴/kg at the time of transplant. Seventeen evaluable patients have been reported with the following diagnoses: ALL (3), AML (6), biphenotypic leukemia (1), CML (1), MDS (1), aplastic anemia (2), congenital amegakaryocytic thrombocytopenia (1) combined immunodeficiency (1), and hemophagocytic lymphohistiocytosis (1).

Twelve of the 17 (65%) were alive and well as of 2010, with follow-up ranging from 3 months to 6.5 years (median follow-up 2.5 years). Survivors include 7/12 (58%) with malignant disease and 5/5 (100%) with non-malignant disease. One patient died at 7 months after transplant due to parainfluenza and Paecilomyces infections and

[figure not shown]
another died at 23 months after transplant due to disseminated Mucor infection, a fungus from the class of Zygomycetes. There was no severe (grade III/IV) acute GvHD. Only 3/17 (18%) of patients achieved > 100 CD4+ T cells/uL by 100 days after transplant and 3/4 of these patients either had received donor T cell infusion for serious viral infections prior to 100 days or had GvHD (in which case the T cells probably represented those causing the GvHD and not providing protection against infection).

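### Time to CD4 and PHA recovery has no estimator, denominator or censoring rule, and the plan's only written default would describe recovered patients alone and report too short a time

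*Combined protocol and SAP*

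**What the plan says.** The Synopsis, under Secondary Endpoint(s), lists for immune recovery "The time to CD4 count >100 and > 200", together with the times to PHA ≥10% and 30%, as quantities to be calculated. It names no estimator and does not say who is in the denominator or what happens to a patient who never reaches the threshold. The only time-to-event method named in that list is for survival: "Overall survival will be estimated using the Kaplan-Meier method". Transplant-related mortality (TRM) is to be given at two time points: "The incidence of TRM will be calculated at Day 100 after transplant and at one year".

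Under Statistical Methodology, the Synopsis gives general reporting rules that name no endpoint: "Continuous variables will be summarized using the mean, standard deviation, median, minimum, and maximum", and "Missing data will not be imputed". Section 10.1 lists immune recovery as a secondary outcome without a method. Section 12 adds only descriptive and subgroup analyses ("Interim descriptive analyses will be performed annually").

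Two other places bear on which recovery times can be observed. Section 4.3 and the Synopsis make disease progression a ground for ending an individual's participation. Follow-up is at least one year in the Synopsis and one year in Section 1.0, but Section 4.4 ends it at day 100.

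**The concern.** A recovery time exists only for patients who recover. If times are pooled as an ordinary continuous variable and absent values are left out, the summary is conditional on having recovered within the observation window. The patients removed are those in whom recovery failed or came late: deaths, relapses, rejections, and those still below the threshold at last contact.

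This matters because the background presents slow immune recovery as a known weakness of the approach. Section 2.1 concludes that reconstitution was slow and that infections contributed to morbidity and mortality, and it reports 37% TRM, mostly from infection, in one cited series. Serving as a platform for faster immune recovery is among the secondary objectives in Section 1.2. A summary of recovered patients only would make this weakness look smaller than it is.

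**Working it through.** The plan gives no figure for immune recovery, so there is none to reproduce. Two checks show the likely size of the effect.

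**1. Denominator effect in the cited series (Section 2.1).** The retrospective series had 18 patients. The protocol reports: "By nine months post-transplant, 10 of the 13 evaluable patients had a CD4 count > 200".
- Evaluable patients: 10/13 = 77%.
- All transplanted: 10/18 = 56%, if none of the five non-evaluable patients had recovered.
- CD4 >100 at three months: 4/15 = 27% of evaluable patients, and 4/18 = 22% of all on the same assumption.

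Follow-up in that series starts at 7 months, so at least one patient may simply not have reached nine months. The 56% is therefore a lower bound.

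**2. Bias in the median if only recovered patients are summarised.** Inputs, with time in months:
- Recovery hazard, from 10/13 by nine months taken as recovery in the absence of competing events: r = −ln(3/13)/9 = 0.163.
- Competing hazard (death or relapse), from an assumed 12-month risk q: d = −ln(1−q)/12, with q = 11%, 19%, 30%, 40%. The first two values match the day-100 mortality and one-year TRM in the cited series, and the higher two allow for relapse.
- Total hazard: g = r + d.
- Window H: 12 months, or 100/30.44 = 3.29 months.

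Formulas:
- Cumulative incidence: C(t) = (r/g)(1 − e^(−gt)).
- Median over all patients (C = 0.5): −ln(1 − 0.5g/r)/g.
- Median among those recovered by H: −ln(1 − 0.5(1 − e^(−gH)))/g.

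For q = 19%: d = 0.0176 and g = 0.1805. The all-patient median is −ln(1 − 0.5 × 0.1805/0.1629)/0.1805 = 4.47. With H = 12, e^(−gH) = 0.1147, and the recovered-only median is −ln(0.5573)/0.1805 = 3.24.

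| q | All-patient median | Recovered-only, 12 months | Gap | Recovered-only, day 100 | Gap |
|---|---|---|---|---|---|
| 11% | 4.37 | 3.33 | 1.0 | 1.41 | 3.0 |
| 19% | 4.47 | 3.24 | 1.2 | 1.40 | 3.1 |
| 30% | 4.64 | 3.11 | 1.5 | 1.39 | 3.3 |
| 40% | 4.85 | 2.98 | 1.9 | 1.37 | 3.5 |

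A simulation of 2,000,000 patients gave the same recovered-only medians.

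Setting d = 0 separates the causes. The all-patient median is ln 2/0.163 = 4.25, and the recovered-only median is 3.44 (12 months) or 1.43 (day 100). Gaps of 0.8 and 2.8 months therefore arise with no deaths or relapses at all. Much of the bias comes from dropping patients not yet recovered.

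With a day-100 window, C(3.29) is only 0.39 to 0.41, so the median could not be estimated from the data. A recovered-only summary would still print about 1.4 months.

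**Sensitivity to constant hazards.** The model puts about 40% of patients above CD4 200 by day 100, yet the cited series had only 27% of evaluable patients above CD4 100 at three months. Real recovery is therefore probably later. Replacing the recovery curve by 1 − e^(−(t/c)²), with c = 9/√ln(13/3) = 7.43, and integrating numerically for q = 11% and 40%, gives gaps of 0.6 to 1.6 months (12-month window) and 4.1 to 4.9 months (day 100). The direction is unchanged.

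**The case against.** The strongest reply is that the plan never says recovery time will be averaged over recovered patients. The Synopsis says only that the time will be calculated, and the rule for continuous variables is generic. That stands: the continuous-variable reading is an inference, and strictly the finding is that the method is unspecified. It does not remove the problem, because no other written rule fits a time in days, and an analyst following the plan would land on that one.

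Three stronger readings are tempting, and the documents do not support them.
- A reader might infer that TRM as a plain incidence is biased because relapse competes with it. With complete follow-up, TRM deaths divided by all transplanted equals the cumulative incidence with relapse as the competing event. It also has no bearing on how fast recovery looks. TRM is at risk only if one-year follow-up is incomplete, which Section 4.4 makes possible.
- A reader might infer that recovery will also look more complete than it is. That depends on a denominator the plan does not state. It would be so for evaluable or surviving patients, but not for a proportion of all transplanted.
- A reader might infer that Kaplan-Meier with deaths censored will overstate recovery. The plan names Kaplan-Meier for overall survival only.

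It is also fair to say that this is a secondary, descriptive endpoint in an uncontrolled study of 30 recipients. No stopping rule or sample size depends on it. That limits the weight of the point, not its validity.

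**Conclusion.** The point holds as an unspecified analysis whose only written default would mislead. If that default is applied, time to CD4 and PHA recovery will be reported as too short. The understatement of the median is about 1 to 2 months with a 12-month window and about 3 to 3.5 months if follow-up ends at day 100.

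Those sizes rest on constant hazards, on a recovery rate taken from 13 evaluable patients, and on assumed competing risks of 11% to 40%. They are illustrations, not predictions. The direction does not rest on them, since conditioning on recovery within a finite window shortens the observed times whatever the hazard shape. The 77% against 56% contrast is the upper end of the denominator effect in that series. No bias in TRM as such is established.

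**What to change.** Add to Section 12:
- Estimate each CD4 and PHA threshold by cumulative incidence (Aalen-Johansen) in all transplanted recipients.
- Treat death before recovery as the competing event. Count relapse, graft failure or second transplant as competing only if prespecified as such.
- Censor patients who are alive and not recovered at last contact.
- Report the estimate at fixed times such as day 100 and one year, and give a median only if the curve reaches 50%.
- Exempt these times from the mean and standard deviation summary in the Synopsis.
- Report TRM over all transplanted recipients, using cumulative incidence with relapse as the competing event if follow-up is incomplete.

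The day-100 end of follow-up in Section 4.4 and the one-year minimum in the Synopsis must be reconciled.

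The analysis change costs a few sentences and standard software. The downsides are that recovery will look slower than under the default summary, and that the one-year estimates can be given only once the follow-up conflict is settled.
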